Feeling Depressed or Tearful	0	1	2	3	4
Feeling Frustrated or Impatient	0	1	2	3	4
Forgetfulness, poor memory	0	1	2	3	4
Poor Concentration	0	1	2	3	4
Taking Longer to Think	0	1	2	3	4
Blurred Vision	0	1	2	3	4
Light Sensitivity,					
Easily upset by bright light.....	0	1	2	3	4
Double Vision	0	1	2	3	4
Restlessness	0	1	2	3	4

Are you experiencing any other difficulties?

1 2 3 4

1. _____ 0

2. _____ 0 1 2 3 4

(ii) Neck Disability Index (NDI)

Neck Disability Index

This questionnaire has been designed to give us information as to how your neck pain has affected your ability to manage in everyday life. Please answer every section and mark in each section only the one box that applies to you. We realise you may consider that two or more statements in any one section relate to you, but please just mark the box that most closely describes your problem.

Office Use Only

Name _____

Date _____

Section 1: Pain Intensity

- I have no pain at the moment
- The pain is very mild at the moment
- The pain is moderate at the moment
- The pain is fairly severe at the moment
- The pain is very severe at the moment
- The pain is the worst imaginable at the moment

Section 2: Personal Care (Washing, Dressing, etc.)

- I can look after myself normally without causing extra pain
- I can look after myself normally but it causes extra pain
- It is painful to look after myself and I am slow and careful
- I need some help but can manage most of my personal care
- I need help every day in most aspects of self care
- I do not get dressed, I wash with difficulty and stay in bed

Section 3: Lifting

- I can lift heavy weights without extra pain
- I can lift heavy weights but it gives extra pain
- Pain prevents me lifting heavy weights off the floor, but I can manage if they are conveniently placed, for example on a table
- Pain prevents me from lifting heavy weights but I can manage light to medium weights if they are conveniently positioned
- I can only lift very light weights

Section 7: Work

- I can do as much work as I want to
- I can only do my usual work, but no more
- I can do most of my usual work, but no more
- I cannot do my usual work
- I can hardly do any work at all
- I can't do any work at all

Section 8: Driving

- I can drive my car without any neck pain
- I can drive my car as long as I want with slight pain in my neck
- I can drive my car as long as I want with moderate pain in my neck
- I can't drive my car as long as I want because of moderate pain in my neck
- I can hardly drive at all because of severe pain in my neck
- I can't drive my car at all

- I cannot lift or carry anything

Section 4: Reading

- I can read as much as I want to with no pain in my neck
- I can read as much as I want to with slight pain in my neck
- I can read as much as I want with moderate pain in my neck
- I can't read as much as I want because of moderate pain in my neck
- I can hardly read at all because of severe pain in my neck
- I cannot read at all

Section 5: Headaches

- I have no headaches at all
- I have slight headaches, which come infrequently
- I have moderate headaches, which come infrequently
- I have moderate headaches, which come frequently
- I have severe headaches, which come frequently
- I have headaches almost all the time

Section 6: Concentration

- I can concentrate fully when I want to with no difficulty
- I can concentrate fully when I want to with slight difficulty
- I have a fair degree of difficulty in concentrating when I want to
- I have a lot of difficulty in concentrating when I want to
- I have a great deal of difficulty in concentrating when I want to
- I cannot concentrate at all

Section 9: Sleeping

- I have no trouble sleeping
- My sleep is slightly disturbed (less than 1 hr sleepless)
- My sleep is mildly disturbed (1-2 hrs sleepless)
- My sleep is moderately disturbed (2-3 hrs sleepless)
- My sleep is greatly disturbed (3-5 hrs sleepless)
- My sleep is completely disturbed (5-7 hrs sleepless)

Section 10: Recreation

- I am able to engage in all my recreation activities with no neck pain at all
- I am able to engage in all my recreation activities, with some pain in my neck
- I am able to engage in most, but not all of my usual recreation activities because of pain in my neck
- I am able to engage in a few of my usual recreation activities because of pain in my neck
- I can hardly do any recreation activities because of pain in my neck
- I can't do any recreation activities at all

Score: ____/50 Transform to percentage score $\times 100 =$ %points

Scoring: For each section the total possible score is 5: if the first statement is marked the section score = 0, if the last statement is marked it = 5. If all ten sections are completed the score is calculated as follows:

Example: 16 (total scored)
50 (total possible score) $\times 100 = 32\%$

If one section is missed or not applicable the score is calculated: 16 (total scored)
45 (total possible score) $\times 100 = 35.5\%$

Minimum Detectable Change (90% confidence): 5 points or 10 %points

NDI developed by: Vernon, H. & Mior, S. (1991). The Neck Disability Index: A study of reliability and validity. *Journal of Manipulative and Physiological Therapeutics*, 14, 409-415

(iii) *Dizziness Handicap Inventory (DHI)*

The Dizziness Handicap Inventory (DHI)

P1. Does looking up increase your problem?	 Yes  Sometimes  No
E2. Because of your problem, do you feel frustrated?	 Yes  Sometimes  No
F3. Because of your problem, do you restrict your travel for business or recreation?	 Yes  Sometimes  No
P4. Does walking down the aisle of a supermarket increase your problems?	 Yes  Sometimes  No
F5. Because of your problem, do you have difficulty getting into or out of bed?	 Yes  Sometimes  No
F6. Does your problem significantly restrict your participation in social activities, such as going out to dinner, going to the movies, dancing, or going to parties?	 Yes  Sometimes  No
F7. Because of your problem, do you have difficulty reading?	 Yes  Sometimes  No
P8. Does performing more ambitious activities such as sports, dancing, household chores (sweeping or putting dishes away) increase your problems?	 Yes  Sometimes  No
E9. Because of your problem, are you afraid to leave your home without having someone accompany you?	 Yes  Sometimes  No
E10. Because of your problem have you been embarrassed in front of others?	 Yes  Sometimes  No
P11. Do quick movements of your head increase your problem?	 Yes  Sometimes  No
F12. Because of your problem, do you avoid heights?	 Yes  Sometimes  No
P13. Does turning over in bed increase your problem?	 Yes  Sometimes  No
F14. Because of your problem, is it difficult for you to do strenuous homework or yard work?	 Yes  Sometimes  No
E15. Because of your problem, are you afraid people may think you are intoxicated?	 Yes  Sometimes  No
F16. Because of your problem, is it difficult for you to go for a walk by yourself?	 Yes  Sometimes  No
P17. Does walking down a sidewalk increase your problem?	 Yes  Sometimes  No
E18. Because of your problem, is it difficult for you to concentrate	 Yes  Sometimes  No
F19. Because of your problem, is it difficult for you to walk around your house in the dark?	 Yes  Sometimes  No

E20. Because of your problem, are you afraid to stay home alone?	 Yes  Sometimes  No
E21. Because of your problem, do you feel handicapped?	 Yes  Sometimes  No
E22. Has the problem placed stress on your relationships with members of your family or friends?	 Yes  Sometimes  No
E23. Because of your problem, are you depressed?	 Yes  Sometimes  No
F24. Does your problem interfere with your job or household responsibilities?	 Yes  Sometimes  No
P25. Does bending over increase your problem?	 Yes  Sometimes  No

Used with permission from GP Jacobson.

Jacobson GP, Newman CW: The development of the Dizziness Handicap Inventory. *Arch Otolaryngol Head Neck Surg* 1990;116: 424-427

DHI Scoring Instructions

The patient is asked to answer each question as it pertains to dizziness or unsteadiness problems, specifically considering their condition during the last month. Questions are designed to incorporate functional (F), physical (P), and emotional (E) impacts on disability.

To each item, the following scores can be assigned:

No=0 Sometimes=2 Yes=4

Scores:

Scores greater than 10 points should be referred to balance specialists for further evaluation.

16-34 Points (mild handicap)

36-52 Points (moderate handicap)

54+ Points (severe handicap)

(iv) Headache Impact Test – 6 (HIT-6)

HIT-6™ Headache Impact Test

HIT is a tool used to measure the impact headaches have on your ability to function on the job, at school, at home and in social situations. Your score shows you the effect that headaches have on normal daily life and your ability to function. HIT was developed by an international team of headache experts from neurology and primary care medicine in collaboration with the psychometricians who developed the SF-36® health assessment tool. This questionnaire was designed to help you describe and communicate the way you feel and what you cannot do because of headaches.

To complete, please circle one answer for each question.

When you have headaches, how often is the pain severe?

never rarely sometimes very often always
▼ ▼ ▼ ▼ ▼

How often do headaches limit your ability to do usual daily activities including household work, work, school, or social activities?

never rarely sometimes very often always
▼ ▼ ▼ ▼ ▼

When you have a headache, how often do you wish you could lie down?

never rarely sometimes very often always
▼ ▼ ▼ ▼ ▼

In the past 4 weeks, how often have you felt too tired to do work or daily activities because of your headaches?

never rarely sometimes very often always
▼ ▼ ▼ ▼ ▼

In the past 4 weeks, how often have you felt fed up or irritated because of your headaches?

never rarely sometimes very often always
▼ ▼ ▼ ▼ ▼

In the past 4 weeks, how often did headaches limit your ability to concentrate on work or daily activities?

never rarely sometimes very often always

▼		▼		▼		▼		▼
	+		+		+		+	
								
COLUMN 1 6 points each		COLUMN 2 8 points each		COLUMN 3 10 points each		COLUMN 4 11 points each		COLUMN 5 13 points each

To score, add points for answers in each column.

If your HIT-6 is 50 or higher:

You should share your results with your doctor. Headaches that stop you from enjoying the important things in life, like family, work, school or social activities could be migraine.

TOTAL
SCORE

©2001 QualityMetric, Inc. and GlaxoSmithKline Group of Companies. All rights reserved.

(v) *Fatigue severity scale (FSS)*

FATIGUE SEVERITY SCALE (FSS)

Date _____ Name _____

Please circle the number between 1 and 7 which you feel best fits the following statements. This refers to your usual way of life within the last week. 1 indicates “strongly disagree” and 7 indicates “strongly agree.”

Read and circle a number.	Strongly Disagree	→	Strongly Agree				
1. My motivation is lower when I am fatigued.	1	2	3	4	5	6	7
2. Exercise brings on my fatigue.	1	2	3	4	5	6	7
3. I am easily fatigued.	1	2	3	4	5	6	7
4. Fatigue interferes with my physical functioning.	1	2	3	4	5	6	7
5. Fatigue causes frequent problems for me.	1	2	3	4	5	6	7
6. My fatigue prevents sustained physical functioning.	1	2	3	4	5	6	7
7. Fatigue interferes with carrying out certain duties and responsibilities.	1	2	3	4	5	6	7
8. Fatigue is among my most disabling symptoms.	1	2	3	4	5	6	7
9. Fatigue interferes with my work, family, or social life.	1	2	3	4	5	6	7

VISUAL ANALOGUE FATIGUE SCALE (VAFS)

Please mark an “X” on the number line which describes your global fatigue with 0 being worst and 10 being normal.

0	1	2	3	4	5	6	7	8	9	10
---	---	---	---	---	---	---	---	---	---	----

Sleep Related Impairment – Short Form 8a

Please respond to each item by marking one box per row.

In the past 7 days...

		Not at all	A little bit	Somewhat	Quite a bit	Very much
Sleep10	I had a hard time getting things done because I was sleepy	 1	 2	 3	 4	 5
Sleep119	I felt alert when I woke up	 5	 4	 3	 2	 1
Sleep18	I felt tired	 1	 2	 3	 4	 5
Sleep25	I had problems during the day because of poor sleep	 1	 2	 3	 4	 5
Sleep27	I had a hard time concentrating because of poor sleep	 1	 2	 3	 4	 5
Sleep30	I felt irritable because of poor sleep.	 1	 2	 3	 4	 5
Sleep6	I was sleepy during the daytime.	 1	 2	 3	 4	 5
Sleep7	I had trouble staying awake during the day.	 1	 2	 3	 4	 5

Sleep Disturbance – Short Form 8b

Please respond to each item by marking one box per row.

In the past 7 days...

		Not at all	A little bit	Somewhat	Quite a bit	Very much
Sleep108	My sleep was restless.....	 1	 2	 3	 4	 5
Sleep115	I was satisfied with my sleep	 5	 4	 3	 2	 1
Sleep116	My sleep was refreshing	 5	 4	 3	 2	 1
Sleep44	I had difficulty falling asleep	 1	 2	 3	 4	 5

In the past 7 days...

		Never	Rarely	Sometimes	Often	Always
Sleep87	I had trouble staying asleep.....	 1	 2	 3	 4	 5
Sleep90	I had trouble sleeping.....	 1	 2	 3	 4	 5
Sleep110	I got enough sleep	 5	 4	 3	 2	 1

In the past 7 days...

		Very poor	Poor	Fair	Good	Very good
Sleep109	My sleep quality was	 5	 4	 3	 2	 1

INTERNATIONAL PHYSICAL ACTIVITY QUESTIONNAIRE

We are interested in finding out about the kinds of physical activities that people do as part of their everyday lives. The questions will ask you about the time you spent being physically active in the **last 7 days**. Please answer each question even if you do not consider yourself to be an active person. Please think about the activities you do at work, as part of your house and yard work, to get from place to place, and in your spare time for recreation, exercise or sport.

Think about all the **vigorous** activities that you did in the **last 7 days**. **Vigorous** physical activities refer to activities that take hard physical effort and make you breathe much harder than normal. Think *only* about those physical activities that you did for at least 10 minutes at a time.

1. During the **last 7 days**, on how many days did you do **vigorous** physical activities like heavy lifting, digging, aerobics, or fast bicycling?

_____ **days per week**

No vigorous physical activities
question 3

Skip to

2. How much time did you usually spend doing **vigorous** physical activities on one of those days?

_____ **hours per day**

_____ **minutes per day**

Don't know/Not sure

Think about all the **moderate** activities that you did in the **last 7 days**. **Moderate** activities refer to activities that take moderate physical effort and make you breathe somewhat harder than normal. Think *only* about those physical activities that you did for at least 10 minutes at a time.

3. During the **last 7 days**, on how many days did you do **moderate** physical activities like carrying light loads, bicycling at a regular pace, or doubles tennis? Do not include walking.

____ **days per week**

No moderate physical activities
question 5

Skip to

SHORT LAST 7 DAYS SELF-ADMINISTERED version of the IPAQ. Revised August 2002.

4. How much time did you usually spend doing **moderate** physical activities on one of those days?

____ **hours per day**

____ **minutes per day**

Don't know/Not sure

Think about the time you spent **walking** in the **last 7 days**. This includes at work and at home, walking to travel from place to place, and any other walking that you have done solely for recreation, sport, exercise, or leisure.

5. During the **last 7 days**, on how many days did you **walk** for at least 10 minutes at a time?

____ **days per week**

No walking

Skip to question 7

6. How much time did you usually spend **walking** on one of those days?

____ **hours per day**

____ **minutes per day**

Don't know/Not sure

The last question is about the time you spent **sitting** on weekdays during the **last 7 days**. Include time spent at work, at home, while doing course work and during

leisure time. This may include time spent sitting at a desk, visiting friends, reading, or sitting or lying down to watch television.

7. During the **last 7 days**, how much time did you spend **sitting** on a **week day**?

_____ **hours per day**

_____ **minutes per day**

Don't know/Not sure

This is the end of the questionnaire, thank you for participating.

SHORT LAST 7 DAYS SELF-ADMINISTERED version of the IPAQ. Revised August 2002.

(ix) EuroQol 5 Dimension (EQ-5D-5L)

Under each heading, please tick the ONE box that best describes your health TODAY.

MOBILITY

- I have no problems in walking about
- I have slight problems in walking about
- I have moderate problems in walking about
- I have severe problems in walking about
- I am unable to walk about

SELF-CARE

- I have no problems washing or dressing myself
- I have slight problems washing or dressing myself
- I have moderate problems washing or dressing myself
- I have severe problems washing or dressing myself
- I am unable to wash or dress myself

USUAL ACTIVITIES (e.g. work, study, housework, family or leisure activities)

- I have no problems doing my usual activities
- I have slight problems doing my usual activities
- I have moderate problems doing my usual activities
- I have severe problems doing my usual activities
- I am unable to do my usual activities

PAIN / DISCOMFORT

- I have no pain or discomfort
- I have slight pain or discomfort
- I have moderate pain or discomfort
- I have severe pain or discomfort
- I have extreme pain or discomfort

[figure not shown]
ANXIETY / DEPRESSION

- I am not anxious or depressed
- I am slightly anxious or depressed
- I am moderately anxious or depressed
- I am severely anxious or depressed
- I am extremely anxious or depressed

- We would like to know how good or bad your health is TODAY.
- This scale is numbered from 0 to 100.
- 100 means the best health you can imagine.
0 means the worst health you can imagine.
- Mark an X on the scale to indicate how your health is TODAY.
- Now, please write the number you marked on the scale in the box below.

YOUR HEALTH TODAY =

The best health
you can imagine

The worst health
you can imagine

(x) Sleep Log

Sample		Consensus Sleep Diary-Core				ID/Name: _____			
Today's date	4/5/11								
1. What time did you get into bed?	10:15 p.m.								
2. What time did you try to go to sleep?	11:30 p.m.								
3. How long did it take you to fall asleep?	55 min.								
4. How many times did you wake up, not counting your final awakening?	3 times								
5. In total, how long did these awakenings last?	1 hour 10 min.								
6. What time was your final awakening?	6:35 a.m.								
7. What time did you get out of bed for the day?	7:20 a.m.								
8. How would you rate the quality of your sleep?	 Very poor  Poor  Fair  Good  Very good	 Very poor  Poor  Fair  Good  Very good	 Very poor  Poor  Fair  Good  Very good	 Very poor  Poor  Fair  Good  Very good	 Very poor  Poor  Fair  Good  Very good	 Very poor  Poor  Fair  Good  Very good	 Very poor  Poor  Fair  Good  Very good	 Very poor  Poor  Fair  Good  Very good	
9. Comments (if applicable)	I have a cold								

(xi) *Participant Satisfaction Questionnaire*

1. Please rate how satisfied you were with the physiotherapy treatment you received.

1	2	3
Not satisfied	Satisfied	Very much satisfied

2. Please rate how satisfied with the frequency of the physiotherapy treatments.

1	2	3
Not enough	Just right	Too much

3. Please rate how satisfied you were with the duration of the treatments.

1	2	3
Too short	Long enough	Too long

4. Please rate how satisfied you were with the time spent with the physiotherapist during the treatments.

1	2	3
Not enough	Just right	Too much

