Study Design: This is a mixed methods feasibility study consisting of 3 parts and will investigate clinician and patient response to a ***simplified physical examination (SPE)*** used to inform post-concussion management. Part 1 (Experimental Study a.), a single-group pretest-posttest clinical design will provide preliminary (pilot) evidence of combined effect of assessment and treatment using the SPE to preselect those suited to manual treatment of the neck. Part 2 (Main Feasibility Study) a mixed methods study will consist of a nested qualitative study examining service providers attitudes toward use of the SPE to identify individuals appropriate for neck rehabilitation following concussion (Orthopedic Manual Treatment (OMT) and neuromuscular/ sensorimotor retraining) and utility of this method in the context of current practice. Quantitative exploration of patient compliance, and satisfaction, as well as any adverse reactions to treatment will also contribute to determining overall feasibility of using the SPE. Part 3 (Experimental Study b.), a 3-month follow up will assess long-term effect of treatment selection based on use of the SPE. Combined evidence from these studies will be used to inform development of a future protocol for a pilot randomised, non-inferiority, controlled trial.

Study Procedure and Setting: Participants will take part in one screening session in the Laboratories located at the School of Physiotherapy, University of Otago, Dunedin (referred to as “*screening session*”). Participants identified as eligible to enter the treatment arm of the study will then be invited to participate in further treatment session (referred to as “*treating sessions*”) where they will attend 2 physiotherapy sessions per week for 4 weeks at physiotherapy clinics local to Dunedin. Follow-up assessment (referred to as “*follow up sessions*”) for participants entering the treatment arm of the study will then be conducted 1 week and 3 months following cessation of treatment and will take place at the University of

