Participants identified as eligible for allocation to the treatment arm of the study will be booked for their initial treatment session a maximum of 2 weeks following the screening session. Participants will be assessed during the first treatment session using an extended standardised assessment of the cervical spine (1 hour). Additional tests of musculoskeletal [31, 71] and sensorimotor function [72] as well as neural mechanosensitivity [73], standard to physiotherapy clinical practice in management of disorders of the neck and concussion [74], in addition to baseline results (provided in report form via post from the SC and supplied to the treating physiotherapist) will inform individualised treatment plans [18, 75]. Following initial assessment by the therapist, participants will receive treatment twice weekly for 4 weeks. During this time participants will also be requested to avoid alternate treatments for their concussion (except for use of prescribed medication/s) to minimise potential for confounding.

Interventions:

Treatment for management of identified neck impairments provided will include OMT (For e.g., Maitland, and Mulligan intervertebral joint mobilisation techniques) neuromuscular and sensorimotor retraining techniques standard to musculoskeletal physiotherapy practice internationally and in New Zealand for management of neck disorders [18, 75]. Individual treatment plans will be pragmatically determined. All participants receiving treatment will be provided with advice and education relating to graduated return to activity and prescribed a sub-symptom threshold cardiovascular exercise program using previously published

guidelines for exercise intensity dose [76]. This adjunct treatment aligns with internationally accepted standards of best practice for concussion management [4].

Treating physiotherapists, up-skilling, and treatment monitoring:

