Clinical data will be entered directly into the study's online data recording form which only the PI, SC and members of the research team will be able to access. Data in this form will be stored under a unique identifier generated during the initial screening session with the SC. Where raw data requires further analysis, it will be deidentified (VR and VNG outcomes) and routinely uploaded to the PIs (OG) password protected laptop or the password protected study laptop. Data collected using VR and VNG will be collected on the devices using the participants unique identifier.

Statistical Analysis

Descriptive analyses will be performed on sociodemographic data. Exploration of central tendency of all data will be evaluated using Kolmogorov-Smirnov and Shapiro-Wilk tests. Where data is significantly skewed, attempts will be made to transform using suggested methods [57]. Individual demographic variables (sex, age, BMI, IPAQ score) which could reasonably be expected to influence quantitative outcomes will be analysed for significance using univariate linear regression and included in models.

Objective 1:

Quantified feasibility outcomes: activity, compliance, and adverse event monitoring

- a. Descriptive statistics will be used for recruitment frequency and the number of eligible participants, the drop-out rate, and degree of missing data for the patient rated and clinical outcomes measures. The programme will be considered feasible if 80% of patients complete the programme until formal discharge based on the physiotherapists' assessment and treatment documentation.
- b. Adherence to the intervention by auditing and summarising patients' logbooks and the physiotherapists' assessment and treatment documentation. The SC will audit the documentation. Adherence will be considered acceptable if 80% of exercises had been recorded in the patient's logbooks.
- c. Adverse events from the treatment will be determined by auditing the physiotherapists' assessment and treatment documentation as well as inclusion of formal reports submitted to the study or HEC in the event of serious adverse events. Number of events will be considered.
- d. Patient satisfaction score (/12) from the patient satisfaction exiting questionnaire will be calculated and mean and 95% CI will be reported.

Triangulation of qualitative (analysis described above) and quantitative outcomes [79] will determine overall feasibility of using the SPE to inform treatment management.

Objective 2:

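### Item 3 of the exit satisfaction form does not say whether it asks about session length or the 4-week course, and the /12 total does not rise with satisfaction

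*Protocol*

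**What the plan says.** The form is in Protocol Appendix 1 (xi), Participant Satisfaction Questionnaire. It has four items, each coded 1 to 3.

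- Item 1: "Please rate how satisfied you were with the physiotherapy treatment you received". The answers run from *Not satisfied* (1) through *Satisfied* (2) to "Very much satisfied" (3).
- Item 2: "Please rate how satisfied with the frequency of the physiotherapy treatments". The answers are *Not enough* (1), *Just right* (2) and *Too much* (3).
- Item 3: "Please rate how satisfied you were with the duration of the treatments". The answers are *Too short* (1), *Long enough* (2) and *Too long* (3).
- Item 4: "Please rate how satisfied you were with the time spent with the physiotherapist during the treatments". The answers are as for item 2.

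The analysis is fixed under Statistical Analysis, Objective 1, point d: "Patient satisfaction score (/12) from the patient satisfaction exiting questionnaire will be calculated and mean and 95% CI will be reported". No recoding of items 2 to 4 is stated.

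On the course itself, Treatment Sessions says that "participants will receive treatment twice weekly for 4 weeks". Satisfaction stands among the quantified feasibility outcomes, under the heading for primary outcomes. Study Design says: "Combined evidence from these studies will be used to inform development of a future protocol".

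**The concern.** Item 3 leaves open which duration is meant. Items 2 and 4 use the word *treatments* for the individual visits, so a patient who reaches item 3 may well take it as the length of a visit. Another patient may take it as the length of the whole course. The two readings call for different action: one bears on how long a session lasts, the other on how long the programme lasts. A designer of the next trial would need to know which was criticised.

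The ambiguity cannot be resolved later. The focus groups and interviews are for health practitioners, so patients are not asked again in their own words. Nor can an analysis plan recover what a patient had in mind when ticking a box.

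The total adds a second difficulty. Item 1 improves as its code rises, whereas items 2 to 4 are best in the middle. A mean of their sum, with its confidence interval, has no clear direction.

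**Working it through.** **1. The protocol's figure.** Four items with a highest code of 3 give 4 × 3 = 12, which reproduces the stated maximum. The lowest possible sum is 4 × 1 = 4.

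**2. What item 3 can mean.**

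| Reading of item 3 | Relation to item 4 | Is the 4-week course covered? |
|---|---|---|
| Length of each session | Overlaps | No item covers it |
| Length of the course | Distinct | Item 3 covers it |

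The form gives no means of telling which row a respondent used. If everyone took the first reading, items 3 and 4 would carry largely one opinion, worth 2 × 3 = 6 of the 12 points. If everyone took the second, there would be no overlap. A mixture is possible and could not be detected.

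**3. What the total measures on the printed codes.** There are 3 × 3 × 3 × 3 = 81 possible answer sets.

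| Patient | Items 1, 2, 3, 4 | Sum |
|---|---|---|
| Top of item 1, middle of items 2 to 4 | 3, 2, 2, 2 | 9 |
| *Not satisfied*, too much or too long throughout | 1, 3, 3, 3 | 10 |
| Top of item 1, too little or too short throughout | 3, 1, 1, 1 | 6 |

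Fifteen of the 81 answer sets score above 9 (ten score 10, four score 11, one scores 12). Each of them contains at least one *too much* or *too long* answer, because item 1 adds at most 3 and three middle answers add 6. So no score above 9 can come from a patient without such a complaint.

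**4. The effect of recoding.** If the middle answer on items 2 to 4 were scored 3 and either end 1, the first patient would move from 9 to 3 + 3 + 3 + 3 = 12. The second would move from 10 to 1 + 1 + 1 + 1 = 4. Recoding would repair the direction of the total but would leave the ambiguity of item 3 untouched.

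**5. Balance of the options.** Item 1 has two favourable options of three. Items 2 to 4 have one each. The form as a whole has 2 + 1 + 1 + 1 = 5 favourable options of 12.

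**6. Size of the item 1 effect on the planned statistic.** Assume that 10% to 30% of respondents are neutral and all tick *Satisfied* (code 2) rather than *Not satisfied* (code 1). The documents give no such share. The mean total then rises by 0.10 × 1 = 0.1 to 0.30 × 1 = 0.3 points of 12. Code 2 is itself the midpoint of the 1 to 3 scale.

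**The case against.** The strongest reply is that the four items run in a sensible order: overall, frequency, duration, contact time. Item 3 has its own answer labels, and only item 4 mentions the physiotherapist. Read in that way, item 3 is about the course and the four questions are distinct. This is a fair reading and may be the intended one. What it does not do is exclude the other, since the item names neither the session nor the course.

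A reader might go further and infer that items 3 and 4 amount to the same question because treatment is given one to one. The protocol does not support that. It also prescribes a cardiovascular exercise programme, and patients log daily home exercise, so treatment time and therapist time can differ.

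A reader might also infer from item 1 that satisfaction as measured here leans positive, which is what the hypothesis predicts. Only item 1 has that imbalance, and items 2 to 4 have more unfavourable options than favourable. The planned result is a mean out of 12, not a share of favourable answers. A rise of 10 to 30 percentage points in such a share would merely restate the assumed proportion of neutral patients.

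Lastly, the consequences are limited. No threshold is attached to satisfaction, and feasibility is judged by triangulating several sources. Completion, drop-out and attendance are measured directly, and item 2 covers frequency. All of this stands and keeps the point minor. It does not make an item 3 answer attributable, and completing a course is not the same as finding its length right.

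An unseen analysis plan might recode items 2 to 4. That would answer the scoring point only.

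**Conclusion.** The point holds as a minor one, in two parts.

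First, item 3 is ambiguous between session length and course length, no item names the course, and an answer at either end cannot be assigned. This rests on the printed wording alone. It would be too strong to say that views on the course are lost altogether: some patients will have read item 3 as course length, but nobody can tell which.

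Second, the total out of 12, taken on the printed codes, does not rise with satisfaction: 9 for the fully content patient against 10 for the dissatisfied one described above. This assumes no recoding, and the protocol states none.

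The lack of balance in item 1 is real but confined to that item. Its effect on the planned mean is 0.1 to 0.3 points under the assumed 10% to 30% of neutral patients.

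**What to change.** Before the form is first used:

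- Reword item 3 to ask about the length of the 4-week programme.
- Reword item 4 to ask about the length of each session with the physiotherapist.
- Under Objective 1, point d, replace the total by item-level results: the distribution of answers to item 1, and the share giving the middle answer on each of items 2 to 4, with exact 95% confidence intervals. Show the counts at both ends of items 2 to 4 as well, since too little and too much point in opposite directions.
- Optionally, give item 1 balanced answers with a neutral option. This is a preference in scale design, and the other changes do not depend on it.

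The cost is two reworded questions and one line of analysis text, with a small departure from the wording of the cited form. The protocol plans no comparison with the study that form came from, so little is lost. If some patients have already completed the form, the reporting change still applies, and their item 3 answers should be presented with the ambiguity stated.
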